Official Title: A PATH (Promoting Activity and Trajectories of Health) for Children

NCT Number: NCT03189862

Document Date: 9/16/2019

IRB Research Plan - HUM00133319

A PATH (Promoting Activity and Trajectories of Health) for Children (Phase I, Cohort 2)
 Science for Behavior Change
 (Based on PROTOCOL HUM0011789)

Ame00094488

The Amendment to HUM00133319 are as follows:

1. Update of [name] affiliation

Objective

a. Objective 1

Physical inactivity in children is a major public health risk factor and national health objective. This National Institutes of Health application 1 R01 HL132979-01 entitled "A PATH (Promoting Activity and Trajectories of Health) for Children" (scored at the 13th percentile) will investigate the immediate and long-term effects of a motor skills - the Children's Health Activity Motor Program (CHAMP) on motor competence, perceived motor competence, and physical activity in preschool-age children. The specific aims are to: 1) examine the immediate post-intervention effect of CHAMP (compared to control participants) on motor competence, perceived motor competence, and physical activity in preschool-age children; 2) assess the sustainable effect of CHAMP (compared to control participants) on motor competence, perceived motor competence, and physical activity across middle childhood; and 3) examine and compare the immediate and long-term mediating effects of perceived motor competence on the relationship between motor competence and physical activity in preschool-age children. We hypothesize that children in CHAMP, compared to control, will demonstrate higher levels of motor competence, perceived motor competence, and physical activity at post-intervention and across the 3-year follow-up. This study will consist of a cluster randomized control trial and CHAMP will be implemented in a predominantly minority and low income population, Head Start preschoolers (N = 300; 3.5-5 years old). Thirty classes of preschool children will be randomly assigned to either the treatment (CHAMP, n = 15) or control (normal preschool free-play/recess, n = 15) condition. The CHAMP intervention will be implemented for (4, 30-minute classes a week or 3, 40-minute classes a week, based on the needs of the school schedule) ~~-30 minutes/day 4 days per week for 30 weeks (~3600 min dose)~~. Data will be collected on: a) 7-day physical activity levels using accelerometry, b) process- and product-oriented motor skill competence c) perceived motor competence.

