
for each child. In CHAMP, children are given opportunities to make choices on specific task engagement, participate in a variety of learning experiences and peer interactions (e.g., cooperative and independent), involve themselves in leadership roles, and are allowed to choose the length of practice time necessary to develop a specific aspect of a skill (i.e., based on personal capabilities).

The CHAMP session is designed to take place in a school gymnasium or large indoor open space (i.e., multipurpose room) that has been designated at each preschool center. The space needed will accommodate 25 – 28 preschool-children and two classroom teachers (i.e., 1 instructor and 1 assistant). For this study, the instructors will be graduate trained movement science specialists. Equipment for the implementation of CHAMP consists of items typically found in preschool movement or early childhood physical education programs or can be obtained for minimal costs (e.g., balls of various sizes, bean bags, cones of various height, striking objects, targets, etc).

Methodology

Research Design. The proposed study is a two arm cluster randomized control trial with follow-up. Classes of children will be randomly assigned to treatment (i.e., movement intervention – CHAMP or the normal movement program provide by their educational center (Control; outdoor free-play activity in a large playground area with a variety of play structures that promote movement and physical activity but no planned instruction nor activities).

Setting and Participants (Recruitment). This study will take place in three Head Start centers (i.e., Perry, Ford, and Beatty) located in Ypsilanti Michigan (Midwest). The racial make-up of the centers are 65.9% Black or African American, 19.14% White (non-Hispanic), 8.82% Hispanic/Latino, 3.26% Asian-Pacific Islander, 2.82 other races (two or more), and 0.06% Native American. Participants will be 300 preschool-age children age 3.5 years and older that encompass diverse settings (30 classes; 15 CHAMP Treatment and 15 Control; 150 preschoolers per condition). Thus, participants will primarily be from urban settings and include low and middle SES black/African American. The three Head Start centers are on the same campus for the three elementary schools (Grades K – 5) where the students will enroll for their formative schooling (i.e., Erickson, Adams Stem, and Holmes Elementary School), which will aid with retention over 3-years of follow-up.

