During the of the study children there is an optional consent requesting that parent/guardian consent to allow their child to be photographed and understand that the photographs maybe use for educational, research, and/or publicity purposes (brochures, CMAH website). Members of the research team ([name], [name], ~~[name]~~ & [name]) will know which children are cleared to be photograph and be the only individuals taking the photographs of the children when engaging in the CHAMP program and when collecting some of the assessment measurement. For past research studies (i.e., at the PI's previous university), a picture of the child engaging the in movement program was included in the Developmental Assessment Report given to parents at the end of the program for those who consented to photo release.

E. Statistical Analysis.

Objective 1 (CHAMP effect on Motor Competence, Physical Activity, and Perceived Motor Competence)

Analysis of Primary Outcomes: Prior to conducting outcome analysis we will examine the range and frequency distributions for all variables, and will transform variables when appropriate. Preliminary analysis will assess each outcome cross-sectionally at baseline and at all follow-up time points. We will compare study groups (i.e., CHAMP vs. Control) for comparability and change in variables over time. To study both the short-term (immediate) and long-term (sustainable) effects of CHAMP, we will assess all longitudinal outcomes by both summary statistics and descriptive data figures over the baseline, post-intervention (month 9) and follow-up at May of Year 2, 3, and 4. Since the samples are collected in different classrooms and different preschools, our data have the clustered structure, which means the within-cluster correlations likely exist. For such clustered longitudinal data, we will use primarily random effects in the following models to account for multi-level correlations among the measurements: Mixed Model Regression (MMR), Growth Curve Modeling (GCM), and Structural Equation Modeling (SEM).⁷⁰⁻⁷³ Random effects are appealing here to account for some latent mediating factors that may exist in the study. We will use MMR to determine the population-average effects of the intervention on primary and secondary outcomes (Aim 1 and

2) and SEM for mediation analysis (Aims 3). [name] (Co-Investigator) has a good deal of expertise on the relevant methodologies and extensive experience on the analysis of multi-level correlated data.

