Growth Curve Models (GCM) will enable us to understand if, and how, time-course changes in MC, PMC, and PA differ between the intervention and control groups. This model is also used to determine a time window over which the intervention effect appears stronger. We will use Structural Equation Models (SEMs) to determine which hypothesized constructs may be responsible for intervention effect on longitudinal PA. Based on the results of our previous work, for example, we hypothesize that PMC will not mediate the relationship between MC and PA at baseline, but PMC will mediate the relationship between MC and PA immediately post intervention and across the 3-yr follow-up period. We will use Mplus software to fit SEMs, and the goodness of fit of SEM models will be assessed using multiple criteria such as Chi-square to degrees of freedom (df) ratio (<2) and the Root Mean Squared Error of Approximation (RMSEA <0.05).

Sample Size, Power Analysis and Sample Attrition. Sample size was calculated based on our primary endpoint, the change in PA between baseline and immediate follow-up. According to previous literature³², we anticipate a change score of 12.1 minutes of MVPA/day for the intervention group after 1 year, with a conservative estimate of the standard deviation (SD) as 27 MVPA/day. Such a change is accepted as a clinically meaningful change in improving PA among preschool children. To detect an adjusted 12.1 (SD=27) difference in PA after 1 year between intervention and control groups with 90% power at an alpha level of 0.05, we will need a total of 212 subjects (106 subjects per arm). To account for a total of a 30% loss to follow-up, we will recruit 298 subjects at baseline (149 subjects per arm). To maintain the statistical power as 90%, the needed sample size and the detectable differences in change of PA scores are summarized in Figure 6.⁶⁹ Cohort feasibility data supports no difficulties identifying subjects who meet initial inclusion criteria for this study (See Approach Section C.4.4.). With the proposed sample size, the relationship between the power we can achieve for analyzing the mean change of MC score and PMC score and their corresponding expected mean difference and SD appears in Figure 7.⁶⁹ Given expected larger effects on MC and PMC, power to detect differences across groups is larger for MC and PMC than that seen with PA.

[figure not shown]

Fig 6: Sample size to achieve 90% power for PA.

[figure not shown]

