Overall Analysis Plans. We will apply transformations to assure normality, run descriptive statistics, and assess potential covariates to include. While maximum effort will be made to retain all participants and minimize the amount of missing data, we anticipate there will be some data lost-to-follow-up and incomplete measures. Therefore, we will address missing data in the analysis plan by applying advanced statistical techniques, such as “multiple imputations” using PROC MI in SAS and IVEWARE SAS macro. Our overall approach will be to employ multivariate analysis to assess associations among key variables using the appropriate models based on the distribution of the data (i.e., normal, categorical data, count data, reaction time data). Since this is a cluster-randomized trial, adjusting the covariates (e.g., child sex, age, race/ethnicity) will aid in controlling additional unbalancesess due to the limited sample size. All analysis will be done using SAS 9.3 or R 4.1.0⁹⁶⁻⁹⁸. Additionally, we will perform “intent to treat”

analysis and assume all subjects comply to the assigned group. Findings/results from the study will also follow the CONSORT guidelines.

Power considerations. When we calculate the sample size and power, we assumed the intra-cluster correlation is 0.3. The achievable power is calculated for a detectable effect size, which is the detectable mean difference standardized by the square root of sample variance. Given the randomization design with 70 children in the intervention group and 50 children in the control group, we have 80% power to detect a difference in cognitive SR, behavioral SR, or emotional SR with an effect size of 0.52 and a Type I error level of 0.05.

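### The 212 children said to give 90% power for MVPA come from an individually randomised calculation, although the trial randomises 30 classes

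*Protocol*

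**What the plan says.** The Protocol, section E (Objective 1, Sample Size, Power Analysis and Sample Attrition), sizes the trial on MVPA: "Sample size was calculated based on our primary endpoint, the change in PA between baseline and immediate follow-up". The inputs are: "To detect an adjusted 12.1 (SD=27) difference in PA after 1 year between intervention and control groups", and the result is "with 90% power at an alpha level of 0.05, we will need a total of 212 subjects (106 subjects per arm"). For attrition it adds: "To account for a total of a 30% loss to follow-up, we will recruit 298 subjects at baseline (149 subjects per arm"). The paragraph gives no ICC, class size, number of classes or design effect.

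Elsewhere the design is plainly clustered. Objective 1 says "Thirty classes of preschool children will be randomly assigned to either the treatment" or control arm, 15 classes each, and Research Design repeats that "Classes of children will be randomly assigned to treatment". Analysis of Primary Outcomes states that "our data have the clustered structure, which means the within-cluster correlations likely exist", and the Aim 1 analysis includes random effects for this reason.

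The SAP has no power section for MVPA. Its only ICC is in the power paragraph for the self-regulation supplement: "we assumed the intra-cluster correlation is 0.3".

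**The concern.** Children in one class share teachers, space, schedule and intervention delivery, so their outcomes tend to be correlated. Each extra child in a class then adds less information than an independent child would. The planned analysis allows for this through its random effects, but the sample size does not appear to. If so, the power quoted for the endpoint that the Protocol calls primary is higher than the planned analysis can deliver.

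A reader who trusts 90% power would take a null MVPA result as fair evidence that no effect of 12.1 min/day exists, when the trial may have had a much smaller chance of finding one. The same paragraph goes on to claim still higher power for motor competence and perceived motor competence.

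**Working it through.** **Inputs from the documents.** Difference 12.1 min/day, SD 27, alpha 0.05, power 90%, 1:1 allocation, 30% loss (Protocol, Objective 1 sample size); 30 classes and 300 children (Protocol, Setting and Participants). Sidedness is not stated.

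**Assumed here.** Equal class sizes and an ICC from 0.01 to 0.30, because the documents give none for MVPA.

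**Step 1: reproduce the plan's figure.**
- Normal approximation, two-sided: n per arm = 2 × [27 × (1.960 + 1.282) / 12.1]² = 104.6, so 105.
- Exact two-sample t-test: 105.6, so 106 per arm (212 in total). Power is 89.8% at 105 and 90.1% at 106.
- One-sided: 86 per arm, which does not match.

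The stated 212 is therefore the two-sided t-test for independent children. The design effect used was 1.

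**Step 2: add the clustering.** With m analysed children per class and N in total:
- design effect DE = 1 + (m − 1) × ICC
- power = Φ[(12.1/27) / √(4 × DE / N) − 1.96]
- difference detectable with 90% power = (1.960 + 1.282) × 27 × √(4 × DE / N)

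As a small-cluster check, power was also computed from a noncentral t with 30 − 2 = 28 df.

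After the planned 30% loss, N = 300 × 0.70 = 210 and m = 7:

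| ICC | DE | Power, normal | Power, 28 df | Detectable difference (min/day) |
|---|---|---|---|---|
| 0 | 1.00 | 90.1% | 88.0% | 12.1 |
| 0.01 | 1.06 | 88.4% | 86.1% | 12.4 |
| 0.05 | 1.30 | 81.3% | 78.5% | 13.8 |
| 0.10 | 1.60 | 72.8% | 69.8% | 15.3 |
| 0.30 | 2.80 | 49.2% | 46.6% | 20.2 |

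With no loss at month 9, N = 300 and m = 10:

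| ICC | DE | Power, normal | Power, 28 df | Detectable difference (min/day) |
|---|---|---|---|---|
| 0.01 | 1.09 | 96.1% | 94.8% | 10.6 |
| 0.05 | 1.45 | 89.7% | 87.5% | 12.2 |
| 0.10 | 1.90 | 80.4% | 77.6% | 13.9 |
| 0.30 | 3.70 | 52.3% | 49.5% | 19.4 |

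**Step 3: break-even ICC (normal approximation).** With 212 analysed, power stays at 90% only up to an ICC of about 0.002, and falls below 80% above about 0.059. With all 300 analysed, 90% holds up to about 0.048 and 80% up to about 0.102.

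**Step 4: what 90% power would take with 30 classes.** About 305 analysed at ICC 0.05 and about 623 at ICC 0.10. Fifteen classes per arm cannot supply an effective 104.6 children per arm at any class size once the ICC exceeds 15 / 104.6 = 0.143.

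**Step 5: loss inflation.** 298 × 0.70 = 208.6, just under 212. The matching recruitment figure is 212 / 0.70 = 302.9, so 303 (304 with equal arms, since 106 / 0.70 = 151.4, so 152 per arm).

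**The case against.** **The attrition may not apply at month 9.** The Protocol's Data Collection section puts the 30% loss over 3 years, while the sizing endpoint is at month 9, so more than 212 children may be analysed. With an assumed 10% loss (270 analysed, 9 per class), power by the same formula is 94% at ICC 0.01, 88% at 0.05 and 78% at 0.10. This stands as a qualification: at small ICCs and low early loss the enrolled sample can exceed 90%. It does not rescue the stated claim, because the sample-size paragraph itself ties 90% power to 212 analysed after a 30% loss. The surplus is reserved for attrition. Complete data are also unlikely, because the endpoint is a change score and valid wear needs at least 9 hours on 3 weekdays and 1 weekend day.

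**The ICC of 0.3 belongs to other outcomes.** It was assumed for self-regulation, whereas MVPA is recorded over a whole week, home and weekend included. That is right. The 0.30 row is an illustrative upper end, not an estimate for MVPA.

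**The SD is called conservative and the difference adjusted.** An SD of 27 / √1.3 = 23.7 in the adjusted model would offset a design effect of 1.3. No such reduction is stated, and the unadjusted t-test already returns 212, so neither word can stand for a clustering allowance. Figures 6 and 7 are not visible, but they cannot change a number that the text's own inputs reproduce.

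**The analysis model is sound.** The random effects address the clustering in the analysis, and this point shows no bias or type I error problem. The error is confined to the stated power.

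**Conclusion.** The concern holds. The 212 is an individually randomised figure applied to a trial of 30 randomised classes, and the 90% power attached to it is not delivered for any ICC above about 0.002. With the planned analysed sample of about 210, power is roughly 88% at ICC 0.01, 81% at 0.05 and 73% at 0.10. It falls to 49% at the illustrative 0.30. Class-level degrees of freedom take off a further 2 to 3 points. The difference detectable with 90% power is 13.8 min/day at ICC 0.05 and 15.3 at 0.10, against the 12.1 that the Protocol calls clinically meaningful.

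These sizes rest on equal classes, 7 analysed children per class, an SD of 27 and an ICC that the documents do not supply. That the calculation omits clustering rests on none of these, because the plan's own inputs reproduce its figure exactly without it. The loss-inflation shortfall (about 209 left against 212 needed) is real but minor. The power statement must be corrected.

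**What to change.** Keep the target of 300 children in 30 classes and rewrite the power paragraph:

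1. Withdraw the statement that 212 subjects give 90% power.
2. State the number of classes, the expected analysed children per class, and an ICC range for change in MVPA (for example 0.01 to 0.30), with a source or a plain statement that none was available.
3. Give power for 12.1 min/day and the difference detectable with 90% power across that range, using DE = 1 + (m − 1) × ICC and class-level degrees of freedom. The tables above can serve as a start.
4. Separate the loss expected by month 9 from the 30% over 3 years, and show power for both.
5. Correct the loss arithmetic: either 212 / 0.70 = 303, or, more simply while keeping 300, state that 298 leaves about 209 and 300 leaves 210.
6. Put the motor competence and perceived motor competence power on the same clustered basis, and carry the paragraph into the SAP, which has none for the main endpoints.

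The cost is wording and a less favourable power statement. No further children, assessments or changes to the analysis model are needed.

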
Data Collection. Trained graduate students external to the project (i.e., not involved in intervention delivery) will collect data using standardized instruments. In August (first month of the academic year), informed consent will be obtained and will be followed by the collection of pretest measures. Based on past experience with large sample data collections ^{10,11,12,13,16,47,48}, we estimate that four, 30 – 35 minute sessions are needed to complete the assessments (e.g., Height, Weight, MC, and PMC, Self -Regulation) for each class and a fifth day will be used for any absences (i.e., make-ups). Physical activity will be measured using accelerometry (ActiGraph) for 7 days to capture the children's engagement during the weekday and weekend. A minimum of 3 weekday and 1 weekend day will be required for data analyses. Accelerometers will be calibrated with individualized measures (i.e., height, weight, sex, and age) collected at pretest. Data collection for both testing periods in year 1 (see project timeline, Table 2) will take a maximum of 6 weeks, which will allow for the 30 weeks of intervention to be implemented. Following initial data collection, physical activity participation and CHAMP will commence. Follow-up assessments will occur at the conclusion of the CHAMP intervention (post-test) end of Year 1 to examine the immediate effect of CHAMP on MC, PMC, and PA. Additional follow-up assessments will be completed to examine the sustainability effect of CHAMP during Year 2 – 4 (Spring of Year 2, 3, and 4).

Data collection in the elementary schools following the preschool intervention year will be facilitated in the same manner as preschool sites. The preschool centers are affiliated with specific elementary schools and are on the campus of the elementary schools. Permission for the project has been provided by the Superintendent, Center Directors, and Principals (see letters of support) of the elementary schools as well. Based on previous longitudinal work³² expected attrition due to relocation issues and/or disinterest in continuing the study will be 30% over 3 years. Thus, our initial oversampling will be 30%. To promote

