Missing Data: Assuming data are Missing at Random (MAR), multiple imputation techniques will be used to replace missing data.⁷⁶ Missing data will be assumed to be MAR if no participant demographics or primary outcomes are correlated with missingness. Mixed effects models allow for partial information to be included for individuals who may dropout prior to any post-intervention data collections. Sensitivity analysis over a range of missing data mechanisms will be performed as necessary. We expect limited missing data because the Michigan research staff will be present to supervise data collection and identify potential problems with missed data. Missing values will be multiply imputed using available covariates by sequential imputation. This approach allows optimal use of available data in analysis involving change measures.

Early Withdrawal/Dropouts: Measures will be taken to retain all participants overtime, however we do expect to loss participants in both the intervention and control groups overtime. A conservative estimate of this attrition rate is 30% during the study period. We plan to implement the intent-to-treat (ITT) analysis.⁷⁷ We will make every effort to collect follow-up data at each time point from individuals who have not withdrawn from the study. Our approach has been to sponsor booster sessions as “classroom reunion/birthday parties” along with rewards and incentives to gather follow-up data. This approach has worked well for bringing kids together to reduce potential dropout.

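### Recruiting 298 does not cover a 30% loss from 212 (303 would): a minor arithmetic error worth about half a percentage point of power or less

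*Protocol*

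**What the plan says.** The calculation is in Protocol section E, Objective 1, Sample Size, Power Analysis and Sample Attrition. The endpoint is given first: "Sample size was calculated based on our primary endpoint, the change in PA between baseline and immediate follow-up". The target follows: "To detect an adjusted 12.1 (SD=27) difference in PA after 1 year between intervention and control groups". The error rates attached to that target are given as "with 90% power at an alpha level of 0.05", and the result is "we will need a total of 212 subjects (106 subjects per arm"). The next sentence gives the recruitment figure: "To account for a total of a 30% loss to follow-up, we will recruit 298 subjects at baseline (149 subjects per arm").

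The 30% appears in two other places. Under Data Collection in section D, expected attrition from relocation and "disinterest in continuing the study will be 30% over 3 years. Thus, our initial oversampling will be 30" (per cent). Under Early Withdrawal/Dropouts in section E: "A conservative estimate of this attrition rate is 30% during the study period".

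The number the trial plans to recruit is 300, with 150 per condition (Setting and Participants). The note on recruitment under Inclusion/Exclusion Criteria confirms 300 as the overall number. The SAP gives no sample-size calculation for Objective 1, so the protocol paragraph is the only source.

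**The concern.** A recruitment figure that allows for loss has one job: once the stated fraction is lost, at least the required number must remain. Here 30% off 298 does not leave 212, and 30% off 300 does not either. The protocol calls 30% a conservative estimate, so a reader would expect some margin at that rate, and there is none.

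What is at stake is the accuracy of a stated property of the design. Anyone checking retention against the protocol would believe that a 30% loss still leaves the required number, when the true limit is slightly lower. No enrolment, analysis or decision rule depends on the difference.

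**Working it through.** **Inputs.** Difference 12.1 min/day of MVPA, SD 27, power 90%, alpha 0.05, 106 per arm (212), 30% loss and 298 recruited, all from the Objective 1 sample-size paragraph. The 300 recruited is from Setting and Participants. The paragraph does not state whether the test is two-sided, nor which formula was used.

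**Step 1: reproduce 212.** By the normal approximation, two-sided:

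n per arm = 2 × [SD × (1.960 + 1.282) / difference]² = 2 × [27 × 3.242 / 12.1]² = 104.64

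This rounds up to 105. The two-sample t-test gives 105.6, so 106 per arm and 212 in total, which is the stated figure. A one-sided test gives 86 per arm by the normal approximation and does not fit. So 212 is reproduced by a two-sided t-test on individually randomised children.

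**Step 2: allow for loss.** The rule is n / (1 − loss).

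- 212 / 0.70 = 302.9, so 303.
- 106 / 0.70 = 151.4, so 152 per arm, or 304 with equal arms.

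The stated 298 is 5 to 6 below this (under or at 2%), and 300 is 3 to 4 below.

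**Step 3: what the planned numbers leave.**

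- 298 × 0.70 = 208.6 (104.3 per arm).
- 300 × 0.70 = 210 (105 per arm).
- Loss that leaves exactly 212: 1 − 212/298 = 28.9%; 1 − 212/300 = 29.3%, which is 88 children.

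**Step 4: effect on power** (two-sided 0.05, difference 12.1, SD 27, no clustering).

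| Retained per arm | t-test | Normal approximation |
|---|---|---|
| 104 (298 less 30%, rounded down) | 89.6% | 89.8% |
| 105 (300 less 30%) | 89.8% | 90.1% |
| 106 (required) | 90.1% | 90.4% |

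**Step 5: where 149 might come from.** The unrounded normal-approximation figure divided by 0.70 is 104.64 / 0.70 = 149.5 per arm, which truncates to 149. That would explain the figure, but the protocol does not show its route.

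**Comparison within the protocol.** Objective 2 requires 98, allows for 16.5% loss and recruits 120. There 98 / 0.835 = 117.4, and 120 × 0.835 = 100.2, so the required number is kept.

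**The case against.** The best case for the plan is that this is rounding. If 149 is the unrounded sample size divided by 0.70 and truncated, the authors used the right rule and lost a few children at the last step, and every resulting power figure still prints as 90%. The trial recruits 300, not 298, and by the normal approximation 300 less 30% still gives 90.1%. The 30% is a loss over three years, whereas the powered endpoint is the immediate post-intervention change at month 9, by which time less of that loss may have occurred. Finally, the protocol plans intention-to-treat analysis, multiple imputation and mixed models that use partial data, so a lost child is not simply removed.

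Most of this stands as regards consequence. It does not make the sentence correct. The protocol states 106 per arm, and a count meant to hold a power floor is rounded up. The paragraph itself applies a total 30% loss to this endpoint. Imputation does not restore full information. Slack at month 9 is also not assured: the Physical Activity section requires at least four valid wear days, including a weekend day, so some children still enrolled may lack a valid primary outcome.

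Three stronger readings are tempting and are not supported:

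- A reader might take "Thus, our initial oversampling will be 30" (per cent) to mean multiplying by 1.3, giving 106 × 1.3 = 137.8, so 138 per arm and 276 in all, and conclude that the protocol holds two incompatible inflation rules. But 276 appears nowhere, and the sentence gives no formula. It reads naturally as shorthand for allowing for 30% attrition.
- A reader might infer that the retention target is unclear. All three places that give a rate give 30%.
- A reader might note that 106 × 1.40 = 148.4 rounds up to 149 and infer a wrong multiplier. This is only a numerical match, and the truncation in Step 5 is at least as plausible.

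**Conclusion.** The recruitment sentence is wrong as written, by a small amount. Retaining 212 after a 30% loss needs 303 children (304 with equal arms); 298 leaves about 208, and the operating target of 300 leaves 210. The cost is about half a percentage point of power or less on the unclustered calculation, and whether 300 reaches 90% depends on the formula (89.8% by t-test, 90.1% by normal approximation). These figures assume a two-sided test, which the protocol does not state but which its 212 implies, and that the full three-year loss has occurred by month 9. With less loss at that point, the shortfall shrinks or disappears.

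A reader might infer that the trial is materially under-recruited because of this slip. The documents do not support that. The absence of any design effect for class randomisation is a separate matter with far more weight. The protocol gives no intra-class correlation for physical activity. Assuming 7 analysed children per class (210/30), so a design effect of 1 + 6 × ICC, power at 105 per arm would be about 88% at an ICC of 0.01, 81% at 0.05 and 73% at 0.10.

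**What to change.** In the Objective 1 sample-size paragraph, replace the sentence on 298 with:

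> 300 children (150 per arm) will be recruited. A 30% loss leaves 210 (105 per arm, about 90% power before allowing for clustering); 212 are retained if loss is at most 29.3%.

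Under Data Collection, reword the oversampling sentence to say that the recruitment target allows for 30% attrition on that same basis.

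The cost is two sentences. Enrolment, design, budget and analysis are unchanged. The stated position becomes very slightly less favourable, and the reader gains a retention limit that can be checked: at most 88 of 300 lost.
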